### **11.3 Safety Blood Collection**

Patients who experience a serious or severe AE should have, at the discretion of the Investigator, a blood sample drawn for safety labs as soon as possible after the AE has occurred.

Additional blood sampling may be performed at any time during the study if warranted to monitor patient safety.

### **11.4 Pregnancy**

Pregnancy in a patient or partner should be reported within 24 hours of the site becoming aware of the pregnancy by fax or email of the Pregnancy Reporting Form in the study reference materials to Catalyst and its designee PhAST Consulting s.r.l. In addition, pregnancy in a patient is also reported on the End of Study CRF. The Investigator must make every effort to follow the patient through resolution of the pregnancy (delivery or termination) and to report the resolution on the follow-up form (Pregnancy Reporting Form: Additional Information) in the study reference materials. In the event of pregnancy in the partner of a study patient, the Investigator should make every reasonable attempt to obtain the woman's consent for release of protected health information.

### **11.5 Urgent Safety Measures**

The regulations governing clinical trials state that the sponsor and Investigator are required to take appropriate urgent safety measures to protect subjects against any immediate hazards that may affect the safety of subjects, and that the appropriate regulatory bodies should be notified according to their respective regulations. According to the European Union (EU) Clinical Trial Directive 2001/20/EC, "...in the light of the circumstances, notably the occurrence of any new event relating to the conduct of the trial or the development of the investigational medicinal product where that new event is likely to affect the safety of the subjects, the sponsor and the Investigator shall take appropriate urgent safety measures to protect the subjects against any immediate hazard. The sponsor shall forthwith inform the competent authorities of those new events and the measures taken and shall ensure that the IEC is notified at the same time." The reporting period for urgent safety measures is the period from the time of signing of the ICF through the completion of the last study visit. Investigators are required to report any urgent safety measures with 24 hours.

	SMA-002	Page 35
---	---------	---------

Examples of situations that may require urgent safety measures include discovery of the following:

- An immediate need to revise IP administration (i.e. modified dose amount or frequency not defined in protocol).
- Lack of study scientific value, or detrimental study conduct or management.
- Discovery that the quality or safety of IP does not meet established safety requirements.

## **12 APPROPRIATENESS OF MEASUREMENTS**

The measures of safety used in this study are routine clinical and laboratory procedures.

The efficacy measure is based on the QoL assessment.

## **13 REPORTING ADVERSE EVENTS STUDY PROCEDURES**

### **13.1 Start of Long Term Study**

An ICF for the Long-Term Study must be signed and dated by the patient and parents for patients with age < 18 years, the Investigator or designee, and witness (if required) before any study-related procedures are performed.

The following procedures are to be performed as schedule for either the Day 0 (in the case where patient was not randomized) or the Day 28 visit for the SMA-001 protocol and can

	SMA-002	Page 36
---	---------	---------

serve as baseline for the Long-Term study. Any procedure not performed for SMA-001 protocol needs to be completed before the patient can be enrolled in this trial.

- Informed Consent for SMA-002;
- Inclusion/Exclusion criteria for the current study must be verified;
- Standard 12-lead ECG after 5 minutes in the supine position;
- Complete physical examination including weight;
- Vital signs (seated position), including SBP, DBP, heart rate, respiration, and body temperature;
- Clinical laboratory tests including hematology, chemistry, and urinalysis;
- Urine pregnancy test in females of childbearing potential only;
- QoL (use data from Day 0 of SMA-001 for those patients not randomized in SMA-001);
- AEs;
- Concomitant medications.

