## 8.2 Safety of Amifampridine and Amifampridine Phosphate

Safety data collected from 1,454 patients or healthy volunteers in controlled study LMS-002 [(Lambert-Eaton myasthenic syndrome LEMS)], controlled and uncontrolled published studies of LEMS or other neurologic conditions, a 3-year safety surveillance study (ATU), and pharmacokinetic (PK) studies demonstrate amifampridine is well tolerated up to and including 80 mg/day (Firdapse Investigator Brochure, [March 2019](#)). The most common adverse events observed from the clinical safety data were perioral and peripheral paresthesias and gastrointestinal disorders (abdominal pain, nausea, diarrhea, epigastralgia). These events were typically mild or moderate in severity, and transient, seldom requiring dose reduction or withdrawal from treatment. In the pharmacogenomic study in healthy subjects (classified as either slow acetylators or fast acetylators), slow acetylators experienced >80% more drug-related AEs compared with fast acetylators (FIR-001).

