### 8.3 Overall Risks and Benefits

Data on amifampridine treatment in 1,454 patients or healthy volunteers support the favorable safety profile of amifampridine (both base and phosphate formulations) at doses up to 80 mg per day. To date, current data demonstrate that amifampridine phosphate has an acceptable tolerability profile with a positive risk-benefit in patients treated with

 Catalyst <small>pharmaceuticals</small>	SMA-002	Page 17
---	---------	---------

amifampridine for patients with LEMS and CMS, but longer-term studies are needed in patients with SMA. Amifampridine phosphate has also been approved for LEMS in the EU since 2009, so there is a well established safety history.

Patients with SMA Type 3 would already have been treated with amifampridine for several weeks as they come from the SMA-001 protocol before entering SMA-002 study. Therefore, the tolerability of amifampridine phosphate and clinical benefit would already be established, minimizing risk.

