10.2 General Statistical Considerations

The following standards will be applied for the analyses unless otherwise specified.

Simple summary statistics (descriptive statistics) for continuous data will be n (number of non-missing observations), mean, median, standard deviation, minimum, and maximum.

The frequency count and percentage will be used to summarize categorical data. Summary statistics will be presented.

Summary statistics for all safety and efficacy variables will be presented.

All data collected will be presented in the by-patient data listings, sorted by site, patient and, where applicable, by study visit.

Change From Baseline (CFB) will be summarized by post-dose time point for efficacy and safety assessments, where Baseline for this Long-Term study is defined as follow:

- **Safety Baseline values (physical exam, ECG, Labs, vitals)**
 - o **Day 0** for patient not randomized in SMA-001 study
 - o **Day 28** for patient randomized in SMA-001 study
 - o If the **screening visit for SMA-002** will be performed on different day from SMA-001 study last visit (i.e. not on Day 0 or Day 28 or on Early termination visit with the full panel of assessments performed), assessments have to be repeated and they will be the baseline values for SMA-002
- **Efficacy Baseline values (QoL)**
 - o **Day 0** for patients that completed SMA-001 study
 - o **Day 0** for patients randomized but that not completed SMA-001 study (for example discontinued on Day 7)
 - o **Day 0** for patients who had QoL for SMA-001 study, however, did not qualify for randomization; however, based on PI discretion, the patient had benefit and were allowed to enrol in the SMA-002 study
 - o **SMA-001 screening** for patients who had QoL performed at Screening visit of the SMA-001 study, and no QoL was performed on Day 0 or thereafter.)

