The Investigator will determine the severity of each AE using grades defined in [Table 1](#) (the event will be recorded on the source documents and AE CRF). Events that are Grades 4 and 5 are serious events and require completion of both an SAE form and AE CRF.

Table 1 - Categories of Severity for Adverse Events

Severity	Description	
Grade 1	Mild; asymptomatic or mild symptoms; clinical or diagnostic observations only; intervention not indicated.	
Grade 2	Moderate; minimal, local or noninvasive intervention indicated; limiting age-appropriate instrumental ADL*.	
Grade 3	Severe or medically significant but not immediately life-threatening; hospitalization or prolongation of hospitalization indicated; disabling; limiting self-care ADL**.	
Grade 4	Life-threatening consequences; urgent intervention indicated.	Note: Grade 4 and 5 adverse events should always be reported as serious adverse events
Grade 5	Death related to AE.	

Activities of Daily Living (ADL)

* Instrumental ADLs refer to preparing meals, shopping for groceries or clothes, using the telephone, managing money, etc.

** Self-care ADLs refer to bathing, dressing and undressing, feeding self, using the toilet, taking medications, and not bedridden.

A Treatment-Emergent Adverse Event (TEAE) is any AE that emerges after the first dose of study drug for the current Long-Term Study. All AEs will be coded using the Medical Dictionary for Regulatory Activities (MedDRA), Version 23.0. All TEAEs will be summarized. Counts and percentages will be presented for each observed System Organ Class (SOC) and Preferred Term (PT) as defined in MedDRA. A patient having more than one TEAE with the same PT will be counted only once in the incidence calculation for that PT. Similarly, if a patient has more than one TEAE in the same SOC, the patient will be counted only once in the total number of patients with a TEAE for that SOC. Each TEAE will be assessed with respect to severity and relationship to treatment. All AEs will be listed, regardless of whether they were study treatment related.

The relationship of an AE will be recorded using the specified relationship categories described in [Table 2](#).

Table 2 - Description of relationship to adverse events categories

Relationship Category	Description

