Not Related	Exposure to the IP has not occurred OR The administration of the IP and the occurrence of the AE are not reasonably related in time OR The AE is considered likely to be related to an etiology other than the use of the IP; that is, there are no facts [evidence] or arguments to suggest a causal relationship to the IP.
Possibly Related	The administration of the IP and the occurrence of the AE are reasonably related in time AND The AE could be explained equally well by factors or causes other than exposure to the IP.
Probably Related	The administration of IP and the occurrence of the AE are reasonably related in time AND The AE is more likely explained by exposure to the IP than by other factors or causes.

The following summary tables will be provided:

1. An overview of TEAEs including the number of TEAEs, related TEAEs, TESAEs, related TESAEs, TEAEs leading to premature discontinuation, TEAEs leading to hospitalization, life-threatening TEAEs, number of patients with at least one TEAE, at least one related TEAE, at least one TESAE, at least one related TESAE, at least one TEAE leading to premature discontinuation, at least one TEAE leading to hospitalization, at least one life-threatening TEAE, and at least one TEAE leading to death
2. Summary of all TEAEs by Primary SOC and PT
3. Summary of all related TEAEs by Primary SOC and PT
4. Summary of all TESAEs by Primary SOC and PT
5. Summary of all related TESAEs by Primary SOC and PT
6. Summary of all TEAEs leading to hospitalization by Primary SOC and PT
7. Summary of all life-threatening TEAEs by Primary SOC and PT
8. Summary of all TEAEs leading to premature discontinuation by Primary SOC and PT
9. Summary of all TEAEs by Primary SOC and PT and maximum severity
10. Summary of all TEAEs by Primary SOC and PT and relationship to treatment.

The following individual data listings will be produced:

1. A listing of all TEAEs
2. A listing of all TESAEs
3. A listing of all IMP related TEAEs
4. A listing of all IMP related TESAEs
5. A listing of all TEAEs leading to hospitalization
6. A listing of all life-threatening TEAEs
7. A listing of TEAEs leading to premature discontinuation
8. A listing of all TEAEs leading to death
9. A listing of all AEs started before the first dose of study drug for the current Long-Term Study

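### No safety baseline pre-dates amifampridine exposure, and run-in adverse events that persist unworsened are listed but not tabulated

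*Protocol*

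**What the plan says.** Protocol section 9.1 makes long-term safety and tolerability the primary objective. Protocol section 8.3 says entrants "would already have been treated with amifampridine for several weeks as they come from the SMA-001 protocol before entering SMA-002 study".

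**Baseline.** Protocol section 13.1 takes the baseline procedures as scheduled "for either the Day 0 (in the case where patient was not randomized) or the Day 28 visit for the SMA-001 protocol". SAP section 10.2 gives three routes for physical examination, ECG, laboratory tests and vital signs:
- Day 0 "for patient not randomized in SMA-001 study";
- Day 28 "for patient randomized in SMA-001 study";
- if SMA-002 screening is on a different day from the last SMA-001 visit, "assessments have to be repeated and they will be the baseline values for SMA-002".

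The Protocol synopsis places Day 0 at the end of the SMA-001 run-in, after dose titration. Protocol section 10.1 also counts adverse events ongoing at entry as part of the safety baseline. For quality of life only, SAP section 10.2 allows the SMA-001 screening value as a fallback.

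**Adverse events.** Under SAP section 10.12.1 a TEAE "is any AE that emerges after the first dose of study drug for the current Long-Term Study"; the table footnotes say started at or after that dose. The ten summary tables, 14.3.1 to 14.3.10, are all restricted to TEAEs. Events with earlier onset go to one listing, 16.2.5.9: "A listing of all AEs started before the first dose of study drug for the current Long-Term Study". Protocol section 11.1 requires ongoing SMA-001 events to be recorded on the AE page, so the data are collected.

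**The concern.** A long-term safety study should let the reader see what patients experience while on the drug. Here each reference point falls after exposure began. A laboratory, blood pressure or ECG change that arose in the run-in is already in the baseline of a patient who was on drug at that visit, so it cannot appear as a change.

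The same holds for adverse events. Protocol section 8.2 states: "The most common adverse events observed from the clinical safety data were perioral and peripheral paresthesias and gastrointestinal disorders". Such reactions can begin in the run-in. Exclusion criterion 7 keeps out patients whose side effects are intolerable, so any reaction carried into SMA-002 is a tolerated one. If it continues without worsening, it is part of the long-term tolerability picture yet has no row in any summary table.

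At stake is how the primary result reads. The TEAE tables describe new onsets in previously treated patients, but the plan does not say so. The pooled mean changes may also mix baselines taken under different treatment states.

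**Working it through.** The plan is descriptive and unpowered, so it has no figure to reproduce. The check has three parts.

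**1. Is any safety baseline before first exposure?**

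| Route (SAP 10.2) | Position | Treatment at that visit |
|---|---|---|
| Day 0, not randomised | end of run-in, after titration | on amifampridine, by the run-in design |
| Day 28, randomised | after the double-blind phase | not stated |
| Repeat at SMA-002 screening | after SMA-001 | not stated |

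None is. Protocol section 10.6.4 also puts the end of the double-blind period at Day 10, which does not fit Day 28 in Protocol section 13.1 and SAP section 10.2. The sections must be reconciled.

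**2. What does the mean change show?** Let g be the share of patients on drug at baseline, and assume a constant drug effect D that is fully present in each of them. On-drug patients contribute a change of 0 and off-drug patients a change of D, so mean change = (1 − g) × D. The documents do not give g.

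| g (assumed) | Share of D visible as change |
|---|---|
| 1 | 0% |
| 0.75 | 25% |
| 0.5 | 50% |
| 0 | 100% |

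This applies to the change columns for laboratory tests and vital signs. The laboratory shift tables and the ECG shift in SAP section 10.12.3 work the same way: an on-drug patient with an abnormality already present falls in an unchanged cell, such as high/high. The shells head the change columns as change from screening, which does not show the treatment state at the reference visit.

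**3. What do the AE tables leave out?** An event that began in the run-in, is ongoing at the first SMA-002 dose and does not worsen is not a TEAE, so Tables 14.3.1 to 14.3.10 do not count it. Planned N is about 12 (Protocol synopsis). If k patients have such an event and no later TEAE with the same preferred term, the shortfall for that term is k/12:

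| k (assumed) | Shortfall in percentage points |
|---|---|
| 1 | 1/12 = 8.3 |
| 2 | 2/12 = 16.7 |
| 3 | 3/12 = 25.0 |
| 6 | 6/12 = 50.0 |

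With no new cases, the tables would show 0/12 for that term. Read as an observed rate, 0/12 suggests a one-sided 95% upper bound of 1 − 0.05^(1/12) = 22.1% (two-sided exact bound: 1 − 0.025^(1/12) = 26.5%), although the reaction is present in k patients.

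If each patient independently enters with a persisting reaction with probability p, the chance that at least one of 12 is left out is 1 − (1 − p)^12: 72% at p = 0.1, 93% at p = 0.2 and 99% at p = 0.3. These values of p are assumptions; the documents give no rate.

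**The case against.** The strongest reply is that this is a declared design choice. The Protocol defines end-of-SMA-001 findings and ongoing events as the baseline, the primary measure is the incidence of TEAEs, and SMA-001 was itself a safety study. An extension baseline is a reasonable way to measure what happens after entry. That stands, and it is why the planned baseline and tables should be kept.

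A reader might infer that the plan hides drug effects altogether. The documents do not support that:
- Observed laboratory and vital-sign values are tabulated beside the changes.
- Table 14.5.2 counts ECG categories at each visit, and physical-examination findings are summarised as counts by visit and as abnormalities by SOC and PT.
- The SAP has no physical-examination shift table, and under Protocol section 15.7 the SAP prevails, so the change problem does not extend to that assessment.
- A high/high cell shows a persisting abnormality. What it lacks is a pre-drug value against which to judge it.
- A randomised patient who was off drug at Day 28 would show the effect as a change. The difficulty there is pooling of unlike baselines, not masking.

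A reader might also infer that run-in events are lost. They are not: Listing 16.2.5.9 shows start date, an SMA-001 flag, ongoing status, severity and relationship for each patient, and a worsened condition is reportable under Protocol section 11.1.

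Nor do the documents show that persisting reactions are common. Protocol section 8.2 goes on to describe these reactions as typically mild or moderate and transient, and one that resolves and starts again after the first SMA-002 dose is a TEAE. Exclusion criterion 5 also keeps clinically significant ECG abnormalities out at entry.

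Finally, SMA-001 is not available here. Whether drug-free safety values exist, and what patients were taking at Day 28, cannot be confirmed.

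**Conclusion.** The point holds in a limited form. No safety baseline precedes first amifampridine exposure. The change summaries for laboratory tests and vital signs, and the ECG shift, therefore show an effect already present in an on-drug patient as no change, and may pool on-drug and off-drug baselines. A run-in event that continues unworsened is collected and listed but is absent from all ten AE summary tables.

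The size for adverse events is 8.3 percentage points of a preferred term per affected patient, assuming 12 patients and no later TEAE of the same term in that patient. The number affected is unknown. For mean changes, the visible share of the effect depends on an unstated mix of baseline treatments and could lie anywhere from 0% to 100% under the constant-effect assumption. Observed levels remain available throughout, so this is a gap in presentation and interpretation, worth closing because it is cheap to close. It does not invalidate the planned analysis.

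**What to change.** Keep the planned baseline and the TEAE tables, and make three additions.

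1. **One SOC/PT table of events present at any time on amifampridine during SMA-002.** Include the events in Listing 16.2.5.9 that began after the first SMA-001 dose and were ongoing at the first SMA-002 dose, plus the TEAEs, counting each patient once per PT. State in SAP section 10.12.1 that Tables 14.3.1 to 14.3.10 show new-onset events in previously treated patients. The Listing 16.2.5.1 shell has a sample TEAE row flagged as started in SMA-001, which does not fit the footnote definition and should be corrected or explained.
2. **A second reference, where SMA-001 pre-run-in values exist.** Add change and shift from that value for laboratory tests, vital signs and the ECG shift of SAP section 10.12.3. Show each patient's baseline source and SMA-001 treatment at baseline in Listings 16.2.6.1 (blood chemistry), 16.2.6.2 (hematology), 16.2.7.2 (vital signs) and 16.2.7.3 (ECG).
3. **Reconcile the AE reporting start.** Footnote f of Protocol Table 1 starts non-serious reporting after the first SMA-002 dose, while Protocol section 11.1 also takes in events ongoing from SMA-001. The new table depends on those events being recorded consistently.

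The cost is slightly more output and a transfer of some SMA-001 data for about 12 patients, including first-dose dates. The AE percentages in the new table can only equal or exceed those in the TEAE tables, so the profile may look less favourable. Item 1 uses events already recorded for SMA-002 and could go ahead even if item 2 proves impossible.

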### 13.2 End of Months 3, 6, 9, 12, 15, 21 and 27 in Long Term Study

The following assessments and procedures will be determined at the end of Months 3, 6, 9, 12, 15, 21 and 27. Each month has a clinic visit window of  $\pm$  1 week. Additional visits are allowed as necessary.

- Assessment of AEs/SAEs;
- Complete physical exam with weight;
- Vital signs (seated position), including SBP, DBP, heart rate, respiration, and body temperature;
- Standard 12-lead ECG after 5 minutes in the supine position;
- Clinical laboratory tests including hematology, chemistry, and urinalysis;
- Urine pregnancy test in females of childbearing potential only;
- Concomitant medications;
- IP accountability of medication;
- QoL

	SMA-002	Page 37
---	---------	---------

All IP should be collected from the patient at each visit, in order to perform drug accountability. The investigator or her/his designee will dispense sufficient amifampridine for daily outpatient administration for 90 days (or 180 days from Months 15 to 27).

Patients may continue to receive amifampridine until the study is terminated, the patient decides to withdraw from the study, or the development program is discontinued for this indication.

